12.3 Follow-up

Subjects will return to the ward 9–11 days after their final dose of trial medication, or 2–4 days after imaging session 3 (whichever is later; PET subjects only) for a follow-up visit. Withdrawn subjects who consent to a follow-up visit will undergo the same procedures (see section 9.4).

The follow-up period may be extended if:

1. a subject has an unresolved AE at the follow-up visit, which, in the opinion of the investigator, merits further follow-up;
2. plasma concentrations of IMP were higher than predicted, and/or the half-life of the IMP was very long, and the investigator considers that additional follow-up is necessary; or
3. new information becomes available that supports an extended follow-up period.

The investigator will decide on the nature of the follow-up. For example, subjects may have a telephone follow-up at which they are asked about AEs, or subjects may be asked to attend extra outpatient visits for additional monitoring of blood levels or effects of IMP, and for extra safety tests. The extra safety tests might include tests that are not described in this protocol. The investigator reserves the right, during or after the study, to repeat safety tests or to do any extra safety tests that are in the best interest of the subjects.

If a subject has an SAE during the study, they will also have an additional follow-up by telephone at 28 days (± 3) days after their final dose of trial medication.

12.4 Methods

Blood collection

Blood will be taken by venepuncture or via a cannula. At HMR, cannulae will be inserted under local anaesthesia with lidocaine 0.5%, for withdrawal of venous blood.

After each blood sample, the cannula will be flushed with 3–5 mL normal saline, to keep it patent. In order to minimise dilution of each subsequent blood sample with normal saline, the following procedure will be used: about 2 mL will be drawn via the cannula into the sampling syringe, and immediately re-injected gently via the cannula. The definitive blood sample will be taken after a 10-second delay.

Additional cannulation (PET subjects only)

On the day of each imaging session, before each PET scan, an additional cannula will be inserted into a forearm vein, as per site standard operating procedures (SOPs), for administration of the radiolabelled tracer [¹⁸F]-IMA601.

An arterial cannula will be inserted to take blood for analysis of the radioligand and metabolites. The details of sampling times and analysis of the arterial samples (done at the imaging centre) will be provided in a PET blood sampling protocol.

Blood volumes of specific types of samples may vary from those described below, but any change to the sample volumes will not cause the total volume of blood taken during the study to exceed that given in section 12.5.

Samples for laboratory safety tests

Blood will be taken for:

- haematology (2 mL in EDTA)
- clinical chemistry (3.5 mL in tubes with a gelatin plug)
- serology and serum FSH (3.5 mL in tubes with a gelatin plug)
- coagulation (3 mL in sodium citrate)

Blood samples will be collected into 13 × 75 mm tubes. Urine will be collected in Universal containers. Samples will then be transferred to the laboratory. For logistical reasons, blood and/or urine samples may be collected in tubes other than those stated above.

Processing and analysis of samples for laboratory safety tests

Processing of samples will be done by the HMR Analytical Laboratory in accordance with the laboratory's SOPs.

The HMR Analytical Laboratory will do safety tests on blood and urine samples using instruments interfaced to a validated laboratory information management system (LIMS). Data from analysers that are not interfaced will be entered manually into the LIMS.

Table 4: Laboratory safety tests

Haematology:	Clinical chemistry:
• haemoglobin (Hb)	• urea
• red blood cells (RBC)	• creatinine
• mean corpuscular volume (MCV)	• uric acid
• mean corpuscular haemoglobin (MCH)	• total bilirubin
• mean corpuscular haemoglobin concentration (MCHC)	• total protein
• haematocrit	• albumin
• white blood cells (WBC) and differential (neutrophils, lymphocytes, monocytes, eosinophils, basophils)	• globulin
• platelets	• alkaline phosphatase (AP)
Coagulation:	• aspartate aminotransferase (AST)
• prothrombin time (PT)	• alanine aminotransferase (ALT)
• activated partial thromboplastin time (aPTT)	• gamma-glutamyl transpeptidase (GGT)
• international normalized ratio (INR)	• glucose*
Urinalysis:	• phosphate
• dipstick: protein, blood, ketones, glucose, bilirubin, urobilinogen, leukocyte esterase, specific gravity, nitrites, pH	• cholesterol
• microscopy: only if dipstick test for protein, blood, leukocyte esterase or nitrites is abnormal	• triglycerides
Serology:	• potassium
• hepatitis B (hepatitis B surface antigen)	• sodium
• hepatitis C antibody	• calcium
• HIV screen (HIV 1 and 2)	• chloride

* fasting [at screening and follow-up]

FSH tests

Serum FSH tests will be done using a chemiluminescent immunoassay method.

Drugs of abuse, alcohol, and cotinine tests

Urine will be tested for drugs of abuse, alcohol, and cotinine according to the laboratory's SOP. Tests will include: amphetamines, cocaine, opiates, cannabis, barbiturates, benzodiazepines, alcohol, and cotinine.

Processing of blood samples for pharmacodynamic analysis

Blood samples (5 mL) will be taken.

Details will be provided in a PBMC sampling manual.

Processing of blood samples for pharmacokinetic analysis

Blood samples (2 mL) will be taken into K₂EDTA tubes, and immediately placed on ice. Samples will be centrifuged at 1500 G for 10 min at 4°C and the plasma divided into 2 aliquots of approximately equal volume (minimum of 250 µL in each aliquot) in screw-capped polypropylene cryotubes. Plasma samples will be frozen at about -80°C or below within 1.5 h after collection, and stored until dispatch to DDS (Cambridgeshire, UK) for analysis.

Physical and neurological examination

Physical and neurological examination will be done by a physician. Complete physical examinations will examine: general appearance; head, ears, eyes, nose and throat; thyroid; lymph nodes; back and neck; heart; chest; lungs; abdomen; skin; and extremities. The following systems will be assessed: cardiovascular, dermatologic, respiratory, gastrointestinal, musculoskeletal and neurological.

Brief physical examinations will be symptom-directed, and include neurological assessment of cranial nerves, motor, sensation, coordination, reflexes, and gait.

Complete neurological examinations will include the following.

Motor system: upper and lower limbs will be inspected for tremor and fasciculation. Tone will be recorded for all limbs as 'normal', 'increased' or 'decreased'. Tendon reflexes will be elicited bilaterally (biceps, triceps, brachioradialis, knee, ankle) and graded 0 (absent even with reinforcement), + or ++ (normal) or +++ (increased). Plantar responses will be recorded as downgoing or equivocal (normal), or upgoing (abnormal).

Romberg test: this test is designed to identify loss of proprioceptive sensation, resulting in a sensory ataxia. The sensory ataxia is accentuated when the subject stands still with both feet together, arms at each side and eyes closed (Romberg Test). If the subject falls or staggers after 1 min, they are considered to have a sensory ataxia (a positive Romberg sign). If the sign is absent, the test will be repeated with the subject standing on the balls of the feet.

Coordination: will be examined using the 'finger–nose' test bilaterally, whereby the subject touches the examiner's finger at a distance of about 50 cm, with his index finger and then touches his nose, as fast as they can.

Direct pupillary reflexes: elicited by shining a torch into the pupil of the eye being tested and noting pupillary constriction (normal). Consensual pupillary reflexes will be elicited by shining the torch in the pupil of one eye and noting pupillary constriction in the contralateral eye (normal).

Height and weight

Height and weight will be measured by trained staff at HMR.

Vital signs

Blood pressure and pulse rate will be measured using SpaceLabs oscillometric equipment. Measurements will be made with subjects in a seated position; subjects will remain seated for at least 5 min before vital signs are measured.

Tympanic temperature will be measured using digital thermometers.

Respiratory rate will be measured by observation of the chest.

Repeat vital signs measurements

During the trial, if vital signs fall outside the ranges in Table 5, a physician will review and decide on an appropriate course of action. The procedure will be repeated only if instructed by a physician.

Table 5: Vital signs ranges

Vital sign	Range
Seated systolic blood pressure	90–140 mm Hg
Seated diastolic blood pressure	40–90 mm Hg
Seated pulse rate	40–100 beats/min
Temperature	35.5–37.8°C
Respiration rate	10–16 breaths/min

If the result of the repeat measurement is still out of range, the investigator will decide on an appropriate course of action.

Standard 12-lead ECGs

12-lead ECGs will be recorded using Mortara ELI250c and ELI280 cardiographs. Each recording will be printed on a single A4 page at paper speed 25 mm/sec and calibrated to 10 mm/mV. Recordings will be made with subjects in a supine position; subjects will remain supine for at least 5 min before the ECG is recorded. PR, RR, QRS and QT intervals will be captured on source documents. QT interval will be corrected using Fridericia's formula (QTcF).

During the trial, if ECG values fall outside the ranges in Table 6, a physician will review and decide on an appropriate course of action. The procedure will be repeated only if instructed by a physician.

Table 6: ECG ranges

ECG parameter	Range
Ventricular rate	35–100 beats/min
QRS	≤ 120 msec
PR interval	110–220 msec
QTcF (men)	≤ 450 msec
QTcF (women)	≤ 470 msec

If the result of the repeat measurement is still out of range, the investigator will decide on an appropriate course of action.

Columbia-Suicide Severity Rating Scale (C-SSRS)

The C-SSRS is a suicidal ideation rating scale used to evaluate suicidality³⁰. The questionnaire will be administered by the investigator or his delegate. The ‘baseline’ questionnaire will be used at screening, and the ‘since last visit’ questionnaire will be used at follow-up.

Structural MRI

Structural MRI acquisition will be performed at Invicro using either a 3 Tesla Siemens (Siemens Healthcare, Erlangen, Germany) or 3 Tesla GE (GE Healthcare, UK) clinical MRI system, and will consist of a structural scanning protocol. MRI scans will be evaluated by a radiologist to exclude any subjects with major pathology or abnormalities. A radiologist will provide a report of each MRI scan to the investigator at HMR.

PET scan

Dynamic PET scans will be performed at Invicro using a Siemens Horizon PET/CT scanner (Siemens Healthcare, Erlangen, Germany). The subjects will be placed in the PET scanner with head padding to minimise movement during the scan. A low dose CT scan will be performed to correct for the attenuation of emitted radiation. Subjects will then receive an IV bolus injection of up to 100 MBq of the [¹⁸F]-IMA601 radioligand. Dynamic emission data will be recorded for up to about 90 min after injection of the radioligand.

Allen's test

If arterial cannulation will be used, the patency of subjects' ulnar and radial arteries in both wrists will be checked, at screening and before insertion of the arterial cannula on scanning days.

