10.7 Assessment of compliance

All subjects will be dosed with ASN51 on the research ward under the supervision of 2 suitably trained members of HMR staff. Mouth checks will be done.

Subjects who will have PET scans will be dosed with radiolabelled tracer, [¹⁸F]-IMA601 at Invicro, under the supervision of suitably trained members of staff, at least one of whom will be a registered physician or nurse.

11 Dietary and lifestyle restrictions

Subjects will abide by HMR house rules while on the ward or at Invicro.

Subjects will receive their doses of ASN51 in the fed and fasted states, as follows.

- On Days 1 and 14, subjects will fast (no food or drink other than water) from midnight on the evening before dosing, until 4 h after dosing.
- On Days 2–10, 12, and 13, the study medicine will be given before a standard breakfast.
- On Day 11, subjects will take the study medicine after a high-fat breakfast consisting of 2 fried eggs, 2 strips of bacon, 2 slices of toast and butter, 4 ounces of hash brown potatoes, and a glass of whole milk. Subjects will start the meal approximately 30 min before dosing, and must eat all of it by at least 10 min before dosing.

Other standard meals and drinks will be provided at appropriate times. Because the timings of on-treatment PET scans may change, meals for PET subjects may be provided at unusual times.

Other than the water required to take the study medicine, water will not be allowed for 2 h before and after dosing (Days 1 and 14 only).

No food or drink containing Seville oranges or grapefruit, and no smoking or use of nicotine-containing products, will be allowed from 7 days before the baseline PET scan (PET subjects) or the first dose of trial medication (PBMC subjects) until the end of the study. No alcoholic drinks will be allowed 48 h before the baseline PET scan (PET subjects) or first dose of trial medication (PBMC subjects), until the end of the study. No caffeine- or xanthine-containing products (eg coffee, tea, cola drinks and chocolate) will be allowed from 24 h before: the baseline PET scan (PET subjects) or the first dose of trial medication (PBMC subjects) until discharge from

the ward; imaging session 3 (if applicable, PET subjects); and the follow-up visit (all subjects). Subjects should be advised to avoid eating food containing poppy seeds from screening until the end of the study, because that can cause a positive drugs of abuse test result.

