13. Full physical and neurological examinations will be done at screening and at the follow-up visit. Brief (symptom-directed) physical examinations will be done at all other timepoints.
14. FSH tests in post-menopausal women (screening only).
15. Weight only at screening visit 2 (MRI; PET subjects only).
16. Vital signs consist of seated systolic and diastolic blood pressure, pulse rate, tympanic temperature, and respiratory rate. Vital signs will be done at the following timepoints.
 - *PBMC-only subjects*: screening; Day -1; predose and at 2, 4, 8, and 12 h postdose on Day 1; before dosing on Days 2–13; before, and at 2, 4, 8, and 12 h after dosing on Day 14; at 24 h (Day 15), 48 h (Day 16), 72 h (Day 17), 96 h (Day 18), 120 h (Day 19), and 144 h (Day 20) after the last dose of ASN51; and at follow-up
 - *PET subjects* will have the same timepoints as PBMC-only subjects, plus additional assessments at: imaging session 1 (baseline) and imaging session 3 (if held on Day 22 or Day 23)TriPLICATE measurements (obtained \geq 5 min apart) will be made at screening. Single measurements will be made at all other timepoints. Measurements should begin with subjects in a seated position, after resting for at least 5 min. Additional unscheduled assessments may be done at the discretion of the investigator. Morning vital signs should always be taken before study drug administration.
17. During the period of residence, ECGs will be recorded at the following timepoints.
 - *PBMC-only subjects*: screening; Day -1; predose and at 2, 4, 8, and 12 h postdose on Day 1; before dosing on Days 2–13; before, and at 2, 4, 8, and 12 h after dosing on Day 14; at 24 h (Day 15), 48 h (Day 16), 72 h (Day 17), 96 h (Day 18), 120 h (Day 19), and 144 h (Day 20) after the last dose of ASN51; and at follow-up
 - *PET subjects* will have the same timepoints as PBMC-only subjects, plus additional assessments at: imaging session 1 (baseline) and imaging session 3 (if held on Day 22 or Day 23)TriPLICATE recordings (obtained \geq 5 min apart) will be made at screening. Single recordings will be done at all other time points. Recordings should be made with subjects in a supine position, after resting for 5 min.

18. Laboratory safety tests consist of haematology, clinical chemistry, coagulation, and urinalysis. Samples are to be taken at screening, Day -1, before dosing on Days 8 and 14, on Day 20, and at follow-up. Samples for clinical chemistry only are to be taken at Imaging session 1.

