16.2.4 General considerations for data analyses

The minimum set of summary statistics for numeric variables will be: n, mean, standard deviation (or standard error), median, minimum, and maximum. 95% confidence intervals (CI) will be presented where appropriate for data interpretation.

Categorical data will be summarised in frequency tables with n and percentage. Summaries of a categorical variable will include all recorded values.

The minimum and maximum values will be presented to the same number of decimal places as the raw data collected on the CRF (or to 3 significant figures for derived parameters). The mean, median and percentiles (eg Q1, and Q3) will be presented to one additional decimal place. The standard deviation (SD) and standard error will be presented to 2 additional decimal places.

‘Baseline’ will be the latest value obtained before IMP administration (predose on Day 1, or Day –1 if not recorded at predose, or screening if not recorded at predose or on Day –1). Out-of-range laboratory tests may be repeated. If a test is out-of-range at baseline and repeated before dosing, the latest repeat value before dosing will be used as baseline. However, if a test is out-of-range and repeated at any other time during the study, the out-of-range value (not the repeat value) will be included in statistical summaries.

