## **12.2 Derived and transformed data**

Baseline will be considered to be the latest value obtained before study drug administration (eg Day 1, pre-dose; or Day –1 if not recorded at pre-dose; or screening if not recorded at pre-dose or on Day –1).

Laboratory data will be reported in standard units. Out-of-range laboratory tests may be repeated. If a test is out of-range at baseline and repeated before dosing, the latest repeat value before dosing will be used as baseline. However, if a test is out-of-range and repeated at any other time during the study, the out-of-range value (not the repeat value) will be included in statistical summaries.

TriPLICATE ECG and vital sign measurements will be made at screening and the mean of the three measurements for each subject will be used for analysis.

TriPLICATE PBMC measurements will be made and the mean of the three measurements for each subject will be used for analysis.

The PK parameters to be derived are given in Appendix B: Pharmacokinetic analysis.

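### Glucose change from baseline compares fasted Day 14 and follow-up values with a Day -1 baseline whose fasting state is uncontrolled

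*Protocol*

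**What the plan says.** Glucose is part of the clinical chemistry panel in Table 4 of protocol section 12.4. Its footnote reads "fasting [at screening and follow-up" and names no other visit.

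Note 18 to the schedule in protocol section 12.1 fixes the laboratory days: "Samples are to be taken at screening, Day -1, before dosing on Days 8 and 14, on Day 20, and at follow-up". PET subjects have one further chemistry sample: "Samples for clinical chemistry only are to be taken at Imaging session 1", which falls between Day -7 and Day -3.

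The protocol (16.2.4) states that baseline "will be the latest value obtained before IMP administration". The SAP (12.2) has the same rule: "Baseline will be considered to be the latest value obtained before study drug administration". Both give the order as Day 1 predose, then Day -1, then screening. Neither makes an exception for an analyte that depends on fasting.

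On meals, protocol section 11 says: "On Days 1 and 14, subjects will fast (no food or drink other than water) from midnight on the evening before dosing". On Day 8 the dose comes before a standard breakfast. The section says nothing about food before the Day -1 or Day 20 samples.

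SAP Table 14.3.5.1 summarises chemistry values with template T_LB2, which has one block for absolute values and one for change from baseline.

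**The concern.** By asking for fasting glucose at one visit before treatment and one after it, the protocol sets up a like-for-like pair. The general baseline rule breaks that pair. Follow-up glucose, which must be fasting, is compared with Day -1, which need not be, and the fasting screening value plays no part in the change column.

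The error has a predictable direction. Any subject who has eaten before the Day -1 sample raises the baseline and so lowers the apparent change at a fasted visit. The trial is open-label with no control group, so no concurrent comparison would show that a shift came from food rather than drug. With at most 6 subjects per group, a few fed subjects can move the mean. The risk is a change column that understates a real rise in glucose or shows a fall that did not happen.

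**Working it through.** **Step 1. Is there a Day 1 chemistry sample?** Note 18 lists screening, Day -1, Day 8, Day 14, Day 20 and follow-up, which is 6 samples. PET subjects add imaging session 1, which makes 7. Tables 7 and 8 (protocol 12.5) plan 6 and 7 chemistry tests at 3.5 mL each:

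- PBMC-only: 6 × 3.5 = 21 mL, as stated. Table total: 12 + 21 + 18 + 3.5 + 60 + 70 = 184.5 mL, as stated.
- PET: 7 × 3.5 = 24.5 mL, as stated. Table total: 12 + 24.5 + 18 + 3.5 + 360 + 64 + 55 = 537 mL, as stated.

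The plan's own counts leave no room for a Day 1 predose chemistry sample.

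**Step 2. Which value becomes baseline?** With nothing on Day 1, the rule moves to Day -1. Screening is used only if Day -1 is missing. The imaging session 1 sample is earlier than Day -1 and does not displace it. The repeat rule, under which "the latest repeat value before dosing will be used as baseline", applies only when the baseline test is out of range and is repeated, so it does not settle fasting state.

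**Step 3. Fasting state by visit**

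| Visit | Role | Fasting state in the documents |
|---|---|---|
| Screening | not used if Day -1 is present | fasting (Table 4) |
| Day -1 | baseline | no requirement; the Day 1 fast begins at midnight before dosing |
| Day 8 predose | post-baseline | before breakfast; no formal fast stated |
| Day 14 predose | post-baseline | fasted from midnight (section 11) |
| Day 20 | post-baseline | none stated |
| Follow-up | post-baseline | fasting (Table 4) |

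The mismatch is explicit for Day 14 and follow-up, probable for Day 8, and not shown for Day 20.

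**Step 4. Size of the offset.** Let G be mean fasting glucose before treatment, r the true mean rise in fasting glucose, f the share of subjects fed at Day -1, and m their mean fed-minus-fasted difference.

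- Mean baseline = G + f × m
- Mean at a fasted visit = G + r
- Observed mean change = r - f × m, so the offset is -f × m

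The documents give neither f nor m. The values of m below are assumptions, in mmol/L:

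| m | offset, f = 0.5 | offset, f = 1 | observed change if r = 0.5, f = 0.5 | observed change if r = 0.5, f = 1 |
|---|---|---|---|---|
| 0.5 | -0.25 | -0.5 | +0.25 | 0.0 |
| 1.0 | -0.5 | -1.0 | 0.0 | -0.5 |
| 1.5 | -0.75 | -1.5 | -0.25 | -1.0 |

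If every subject happens to be fasting at Day -1, f = 0 and the offset is 0. A rise equal to f × m is cancelled exactly.

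**The case against.** The strongest reply is that this affects one column for one routine analyte in a descriptive table. That stands. The trial tests no hypotheses, T_LB2 has no standard error, confidence interval or test, and neither the stopping criteria nor the criteria for proceeding to Group 2 name glucose or its change from baseline.

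A reader might infer more than the documents support, in four ways.

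- *That the baseline is a fed value.* Table 4 sets no fasting requirement at Day -1, but nothing says that subjects have eaten, and neither the clock time nor the meal timing of that sample is given. The state is uncontrolled; it is not known to be fed. The f = 1 column is the extreme case.
- *That a rise would be hidden from the report.* T_LB2 also tabulates absolute values by time point. The SAP further plans out-of-range summaries, an out-of-range chemistry listing with a clinical-significance flag, and complete listings of all data. Change from baseline is therefore not the only evidence on glucose.
- *That all later samples are fasted.* Day 20 has no stated food condition, and Day 8 has no formal fast.
- *That the bias can be given as a number of standard errors.* This would need an assumed SD of change, which would probably be larger if meal timing varied at Day -1, and there is no planned inference to distort.

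Two further cautions hold. SAP sections 6 and 17 refer to a file note that changed scheduled timepoints; it is not among the documents, so an effect on laboratory sampling cannot be excluded. A screening baseline is also older than Day -1 and would still leave Day 20 without a matched comparator.

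None of this removes the mismatch. Followed as written, the rule does not use the fasting comparison that the protocol provides for.

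**Conclusion.** The point holds as a minor one. The schedule and the baseline rule together make Day -1 the glucose baseline, with fasting state uncontrolled, while Day 14 predose and follow-up are fasted and Day 8 predose probably is. Glucose change from baseline at those visits carries an offset of -f × m, which is zero or negative as long as eating raises glucose. Its size is unknown. The range of -0.25 to -1.5 mmol/L rests wholly on m between 0.5 and 1.5 mmol/L and f of 0.5 or 1. The consequence is confined to the change block of Table 14.3.5.1. The conclusion assumes that the file note did not add a Day 1 chemistry sample or a fasting requirement at Day -1.

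**What to change.** In SAP 12.2 and template T_LB2, calculate glucose change at the fasted visits (Day 14 and follow-up) from the fasting screening value, and show it beside the Day -1-based change. Add a footnote to Table 14.3.5.1 giving the fasting status of each visit, including that none is stated for Day -1 and Day 20.

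This needs a sentence in the SAP and one extra block for one analyte, with no new samples. The downside is an older baseline: screening can be up to 28 days before the first dose for PBMC-only subjects, and for PET subjects up to 21 days before an imaging session that is itself up to 7 days before the first dose (21 + 7 = 28). Showing both changes lets the reader weigh age against fasting state.

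Alternatively, specify in Table 4 that the Day -1 chemistry sample is taken fasting. The existing baseline rule could then stay, but this changes the protocol and helps only subjects not yet sampled.
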